2.3.2. Benefit Assessment

Amoxicillin-clavulanic acid continues to be a reliable antibiotic for the treatment of ARTIs in children caused by amoxicillin-clavulanate susceptible organisms. Worldwide amoxicillin clavulanic acid has shown to be highly effective clinically in Phase III clinical trials in children including infections caused by PRSP and beta lactamase producing pathogens such as *H. influenzae* and *M. catarrhalis*.

The safety profile is well-defined and supported by over 40-years of post-marketing experience. The most commonly occurring events reported in children are mild transient gastrointestinal effects. Clinical and post marketing surveillance data has also shown a good safety profile that is similar across all AMC/CVA pediatric formulations.

More detailed information about the known and expected benefits and risks and reasonably expected adverse events of Augmentin (ES)-600 may be found in the Prescribing Information.

2.3.3. Overall Benefit: Risk Conclusion

Optimizing the PK/PD (ie, T>MIC values) of Augmentin (ES)-600 maximizes bacterial eradication *Streptococcus pneumoniae* (including penicillin-resistant *S. pneumoniae* (PRSP); MIC 2-4 ug/mL), *Haemophilus influenzae* (*H. influenzae*) and *Moraxella catarrhalis* (*M. catarrhalis*); principal respiratory pathogens implicated in ARTIs in children. This assures highest probability of clinical cure, thus reducing the spread and development of resistance.

Thus, it can be considered that the investigation of the safety and clinical efficacy of Augmentin (ES)-600 justified in children having ARTIs with a positive benefit/risk ratio.

Considering the measures taken to minimize the risk to participants in this study, the potential risks identified in association with Augmentin (ES)-600 are justified by the anticipated benefits that may be afforded to patients with ARTIs.

3. OBJECTIVES AND ENDPOINTS

The objectives and endpoints of the study are provided in [Table 2](#) below:

Table 2 Objectives and Endpoints

Objectives	Endpoints
Primary	Primary

 The primary objective of the study is to assess treatment-emergent adverse events (TEAEs) in children receiving Augmentin (ES)-600 (AMC/CVA 14:1) at 90/6.4 mg/kg/day in two divided doses, administered for 10 days in ARTIs(AOM, ABRS or CABP). 	
 Safety will be evaluated by assessing the incidences of treatment emergent adverse events (TEAE).[§]

 The secondary objective of the study is to assess clinical efficacy and incidence of protocol defined diarrhoea (PDD)* in children receiving Augmentin (ES)-600 AMC/CVA 14:1 at 90/6.4 mg/kg/day in two divided doses administered for 10 days in ARTIs (AOM, ABRS or CABP). 	
 Efficacy assessment* will be based on: 
 Early clinical response at the on-therapy visit (Day 3 to 5), defined in terms of 'success' or 'failure' to study intervention. Primary clinical response at the end-of-therapy visit (Day 12 to 14), defined in terms of 'success' or 'failure' to study intervention Secondary clinical response at follow-up (day 22 to 28) ie, 'success' or 'failure'. Incidence of protocol-defined diarrhea (PDD)** in children receiving Augmentin (ES)-600 (AMC/CVA 14:1) at 90/6.4 mg/kg/day in two divided doses administered for 10 days in ARTIs (AOM, ABRS or CABP).

[§]A treatment-emergent adverse effect (TEAE) is defined as an AE which has its onset date on or after treatment start date and on or before treatment stop date + 1 day. All adverse events (AEs) experienced during the same period will be monitored. The detail is described in Section 8.3 “Adverse Events and Serious Adverse Events”.

**Protocol-defined diarrhoea is:

- 3 or more watery stools in one day OR
- 4 or more loose/watery stools in one day OR

- 2 watery stools per day for two consecutive days OR
- 3 loose/watery stools per day for two consecutive days.

* Efficacy assessment will be made using following criteria:

- **Early or Primary Clinical Response**

Success	Clinical cure	Sufficient resolution or improvement of the signs and symptoms such that no additional antibiotic therapy is indicated.
	Improvement	Improvement in at least 1 presenting sign/symptoms. No additional antibiotic indicated.
Failure	Clinical failure	Non-improvement or deterioration in any sign/symptoms after 2 or more days of therapy. Additional antibiotic therapy is indicated.
	Unable to determine	A valid assessment of clinical outcome could not be made (eg, participant did not attend or consent to clinical examination or lost to follow-up).

- **Secondary Clinical Response**

Success	Persistent clinical cure*	Sufficient resolution of signs/symptoms for those participants who were clinically cured or improved at the end of therapy. No additional antibiotic indicated.
Failure	Clinical recurrence	Reappearance of signs/symptoms for those participants who were clinically cured or improved at the end of therapy. Additional antibiotic therapy is indicated.
	Unable to determine	A valid assessment of clinical outcome could not be made (eg, participant did not attend end of therapy visit, or extenuating circumstances or lost to follow-up).

* Participants who showed 'improvement' at EOT (ie, clinical 'success') and remained same at FU without requiring additional intervention, will be categorized as 'persistent clinical cure'.

4. STUDY DESIGN

4.1. Overall Design

This study is an open label, multicentre, non-comparative study. Participants will be children aged between 6 months to 12 years, presenting with ARTIs including AOM, ABRS and CABP.

At Preliminary Visit (Day 0) after signing the informed consent form by the parent/guardian and assent form by children between 7 to 12 years of age, a series of screening evaluations will be performed (Section 5.4.2) including laboratory and radiographic evaluations, in order to determine whether prospective study participant meets the inclusion criteria. Enrolled participants will receive supervised first dose of study intervention from the participant pack. Dosing will be accompanied by demonstration/instruction on reconstitution procedure, product handling, storage, and

accountability (Section 6.2). Additional information on the same will be included in Study reference manual.

Visit 1 can be completed on the same day as the preliminary visit (Day 0) if the laboratory test results and radiological evaluation [Only if needed by investigator's discretion] are available on the same day. All participants will receive Augmentin (ES)-600 at 90/6.4 mg/kg/day administered in two divided doses, every 12 hours with food for 10 days.

The incidence of protocol-defined diarrhoea will be determined from information collected from the Patient Diary cards, which will be appropriately translated for all languages required based on sites participating in the trial. Protocol-defined diarrhoea is:

- 3 or more watery stools in one day OR
- 4 or more loose/watery stools in one day OR
- 2 watery stools per day for two consecutive days OR
- 3 loose/watery stools per day for two consecutive days.

After a minimum of two treatment days (four doses) of study intervention has been taken, an 'on-therapy' (OT) visit will be scheduled between Day 3 and 5.

During this visit, the investigator/study coordinator shall assess safety (primary endpoint) and 'early clinical response' (secondary endpoint). Safety parameter includes treatment-emergent adverse events (TEAEs) for primary study objective. Additionally, clinical status, study intervention compliance, completion of Patient Diary cards, and concomitant medications use will also be assessed. The Investigator will assess safety parameters and clinical status whereas study coordinator will check other parameters with coordinated effort.

Participants with clinical 'failure' or having PDD or severe AE or SAE at OT visit (Day 3 to 5), will be withdrawn from the study intervention (as per Investigator discretion) and treated appropriately. In such case, the OT visit will be considered as End of Therapy (EOT), and all evaluations that are planned at scheduled EOT (Day 12 to 14) will be completed in this visit. However, these participants will return at FU visit (Day 22 to 28) for safety assessment.

Participants with clinical 'failure' or having PDD or severe AE or SAE *after* OT visit (Day 3 to 5) but prior to EOT, will be scheduled to return to the site for an interim evaluation, within 24 hours of notification to the Investigator. Subjects will then be withdrawn from the study intervention (as per Investigator discretion) and treated appropriately. In such case, the interim visit will be considered as EOT visit, and all evaluations that are planned at scheduled EOT (Day 12 to 14) will be completed in this

visit. However, these participants will return at FU visit (Day 22 to 28) for safety assessment.

The participants continuing in the study will return for the scheduled ‘end of therapy’ (EOT) evaluation between Day 12 and 14. The Investigator will enquire the participant or parent/legal guardian about development of AEs and use of concomitant medication(s). The Investigator will perform safety (primary endpoint) and primary clinical response (secondary endpoint) evaluation. Patient Diary cards and unused medication will be returned at this visit.

Participants who experience recurrence of signs/symptoms *after* EOT visit (Day 12 to 14), but prior to scheduled FU visit (Day 22 to 28) will be required to visit the study site twice post EOT - once for the interim visit at the time of any recurrence (Day 15 to 21) and for the scheduled FU visit (Day 22 to 28). At the interim visit, all the evaluations which are to be performed at scheduled FU visit will be conducted. However, in such cases, all evaluations except secondary clinical response will be repeated at scheduled FU visit (Day 22 to 28). All participants experiencing recurrence post EOT will be treated according to the Investigator’s discretion.

All participants, including withdrawals or clinical ‘failures’ at EOT or had disease recurrence after EOT, will return for scheduled FU visit on Day 22 to 28. This visit is required for safety assessment and administration of additional medication, if warranted.

The participants continuing in the study will return for the scheduled ‘follow-up’ (FU) visit between Day 22 and 28. The visit be considered as ‘end of study’ visit, where the Investigator will perform final safety (primary endpoint) and secondary clinical response (secondary endpoint) evaluation (except for recurrence) during the visit.

In general, FU visit at Day 22 to 28 includes both safety and efficacy assessment for participants who were clinical ‘success’ at EOT, but only safety assessment for the participants who were clinical ‘failures’ at EOT or had disease recurrence after EOT. These participants are, by definition, clinical failures at follow-up visit.

4.2. Scientific Rationale for Study Design

As a commitment of receiving Augmentin (ES)-600 marketing authorization from Indian regulators on 08 June 2020, GSK India will have to conduct a Phase IV clinical study in the Indian population. Being a phase IV study, assessment of adverse event profile of Augmentin (ES)-600 would be considered as primary objective. Assessment of clinical efficacy would be considered as secondary objective in this study.

The purpose of this study is to confirm the safety and efficacy profile of Augmentin (ES)-600 in the paediatric population in India, administered at 90/6.4 mg/kg/day in two divided doses for 10 days in ARTIs.

The current study design is a single arm, open-label, non-comparative study, and is based on several GSK-sponsored studies conducted in the past.[SB Report No. [HH-1017/BRL-025000/2/CPMS-382](#)] [SB Report No. [BRL-025000/RSD-1006FN/3/CPMS-446](#)] [SB Report No. [BRL-25000/RSD-1009XZ/3/CPMS-447](#)] [SB Report No [BRL-025000/RSD-1016FL/2/CPMS-536](#)] [[SEIKEL K et al, 1997](#)]

4.2.1. Participant Input into Design

There was no input from participants/participant organisations into the design of this study.

4.3. Justification for Dose

Augmentin (ES)-600, (AMC/CVA 14:1) was chosen to provide an increased dose of amoxicillin that would be enough to treat ARTIs (AOM, ABRS and CABP) not only due to PSSP/PISP, but also due to PRSP (MIC 2-4 μ g/mL). This formulation is also effective against respiratory pathogens like beta-lactamase-positive or negative *H. influenzae* and *M. catarrhalis*.[[AUGMENTIN ES-600 Prescribing Information, 2019](#)]

High dose amoxicillin with or without clavulanic acid has been recommended as preferred therapy in ARTIs, including AOM (AAP 2013/2019), ABRS (IDSA 2012) and CABP (AAP 2004, BTS etc). The selection of high-dose AMC/CVA has been made based on long-term safety of the drug; its efficacy against the key respiratory pathogens in children and a first intention-to-treat PRSP strains and where beta-lactamase producing organism cannot be ruled out.

The Indian National Treatment Guideline 2016 also mentions use of high-dose AMC/CVA (14:1) at 90/6.4 mg/kg/day in (AOM).[[National Treatment Guidelines for Antimicrobial Use in Infectious Diseases, 2019](#)]

Augmentin (ES)-600 is recommended for dosing at 90/6.4 mg/kg/day in two divided doses every 12 hours for 10 days, in children aged 3 months and older. There is no experience in paediatric patients weighing > 40 kg or in adults. There are no clinical data in children under 3 months of age.[[AUGMENTIN ES-600 Prescribing Information, 2019](#)]

4.4. End of Study Definition

A participant is considered to have completed the study if he/she has completed all phases of the study including scheduled FU visit (Day 22 to 28) and excludes those who are early treatment failures and do not complete all visits.

The end of the study is defined as the date of the last visit of the last participant in the study or last scheduled procedure shown in the Schedule of Activities (SoA) for the last participant in the study.

5. STUDY POPULATION

5.1. Inclusion Criteria

Participants are eligible to be included in the study only if they meet all the below inclusion criteria:

1. Age: 6 months to 12 years of either gender.

2. **Diagnosis of AOM on basis of otoscopic findings as defined below:**

- Purulent otorrhea of less than 24 hours duration
- OR
- Middle ear effusion (MEE)
 - Middle ear effusion is evidenced by at least two of the following:
 - Decreased or absent tympanic mobility measured by pneumatic otoscopy,
 - Yellow or white discoloration of the tympanic membrane, or
 - Opacification of the tympanic membrane.

PLUS

At least one of the following indicators of acute inflammation:

- Ear pain within 24 hours, including unaccustomed tugging or rubbing of ear,
- Marked redness of the tympanic membrane, or
- Distinct fullness or bulging of the tympanic membrane.

OR

Child with ABRS with inflammation as bacterial infection who has the following symptoms/signs on the day of or the day before the first dose of the investigational product:

- Redness of the nasal mucosa
- Nasal or postnasal discharge is purulent or mucopurulent
- Pathological shadow in the paranasal sinus on a radiogram (only for reference-based on investigator discretion). Patient with surgical history should be excluded but patient with a previous surgery more than 365 days before and apparently preserved maxillary sinus mucosa or patient with a previous surgery of nasal polypectomy more than 90 days before may be enrolled in the study.

- Child with ABRS whose severity is classified as moderate or severe (total score ≥ 4) based on the nasal cavity findings and symptoms as shown below.

		None	Mild/small amount	Moderate or severe
Symptom	Rhinorrhoea	0	1	2
	Bad mood/ productive cough	0	1	2
Nasal cavity finding	Nasal/postnasal discharge	0 (Serous)	2 (Mucopurulent, small amount)	4 (Moderate or larger amount)

The severity of condition will be determined by the total score of the above symptoms/findings:

1 to 3 = mild, 4 to 6 = moderate, 7 to 8 = severe.

OR

Child diagnosed with CABP based on following criteria: (At least three of the four criteria should be met to include in the study)

- i. History of documented fever (rectal, ear, or oral temperature $\geq 38^{\circ}\text{C}$ or axillary temperature $\geq 37.5^{\circ}\text{C}$) or hypothermia (rectal, ear, or oral temperature $<35^{\circ}\text{C}$ or axillary temperature $<34.5^{\circ}\text{C}$)
- ii. Acute onset or worsening within the previous 5 days of at least two of the following nine clinical signs and symptoms:
 - cough,
 - tachycardia, defined as follows:
 - 6 months to <24 months: ≥ 160 beats/min
 - 24 months to <10 years: ≥ 140 beats/min
 - ≥ 10 years: ≥ 100 beats/min
 - tachypnea, defined as follows:
 - 6 months to <12 months: ≥ 50 breaths/min
 - 12 months to <5 years: ≥ 40 breaths/min
 - ≥ 5 years: ≥ 20 breaths/min
 - dyspnea,
 - grunting,
 - sputum production,
 - chest pain,
 - cyanosis,
 - increased work of breathing
- iii. At least one of the five following laboratory findings:
 - leukocytosis ($>15,000$ white blood cells/ mm^3),
 - $>15\%$ immature neutrophils (bands) regardless of total peripheral white blood cell (WBC),

- leukopenia (4,500 WBC/mm³) and
- iv. Presence with new infiltrates consistent with bacterial pneumonia including new alveolar or lobal infiltrate or consolidation (based on imaging result) - based on investigator's discretion only
- 3. The participant and parent(s)/legal guardian(s) are willing and able to comply with the study protocol.
- 4. In accordance with regional/local laws and regulations, the parent(s)/legal guardian(s) has given signed informed, dated consent; and the participant has given written assent, if applicable, to participate in the study.

5.2. Exclusion Criteria

Participants will be excluded from the study if they meet any of the following exclusion criteria:

1. Weight \geq 40 kg
2. Pre-existing renal insufficiency (eg, plasma creatinine >1.5 times upper limit of normal range for age)
3. Pre-existing liver disease(s) and/or hepatic dysfunction
4. A serious underlying disease as per clinician's judgment.
5. Currently having diarrhea at the time of screening
6. Concomitant infection which would preclude evaluation of the response to study intervention.
7. Concomitant condition precluding evaluation of clinical response (such as acute mastoiditis, facial palsy, bacterial meningitis, and brain tumor) that would preclude evaluation of the response to study intervention.
8. Congenital disorders such as maxillofacial dysplasia.
9. Spontaneous perforation of the tympanic membrane and drainage for longer than 24 hours.
10. Tympanoplasty tube(s) in place, or has anatomic abnormalities associated with recurrent AOM, prolonged middle ear effusion, including cleft palate or repair, high-arched palate, or Down's syndrome.
11. Severe cases of CABP including Hypoxemic, Septic, Ventilator-associated or hospital-acquired pneumonia
12. Need corticosteroid for systemic (inhalational steroids as controller therapy in asthma is allowed)
13. Infectious mononucleosis
14. Evidence of leukopenia and/or thrombocytopenia.
15. History of previous hypersensitivity reaction to penicillins, cephalosporins or other Beta-lactam antibiotics.
16. History of AMC/CVA-associated cholestatic jaundice/hepatic dysfunction.
17. History of phenylketonuria or a known hypersensitivity to aspartame.

18. Received, within 48 hours of study entry, or is scheduled to receive during the study period, any medication which may alter bowel function.
19. Currently receiving or has received more than one dose of systemic antibiotic therapy within one week prior to the initiation of the study.
20. Receipt of an investigational compound (non-FDA and non-DCGI approved) or device within the previous 30 days or five half-lives, whichever is longer, preceding the first dose of study intervention or during the study.
21. Participants with symptoms suggestive of active COVID-19 infection (ie, fever, cough, etc).
22. Participants with known COVID-19 positive contacts within the past 14 days.

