8.2.4. Radiographic Evaluations (X Ray)

An X ray will be performed only at preliminary visit at the study site. Chest X ray and X ray of nasal/paranasal sinus to be performed for patients presumed to have CABP and ABRS. The X ray is not mandatory and performed only for reference, as per investigators discretion. The purpose of radiographic evaluation is only to confirm the diagnosis when CABP or ABRS clinically, reasonably suspected but can't be confirmed with clinical criteria. Since children demonstrates signs and symptoms of CABP differently than adults and may deteriorate more rapidly than adults, keeping an option of chest X ray in the inclusion criteria is critical for investigators to rule out any need for hospitalization.

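### Exclusions 14 and 21 conflict with the CABP entry criteria: leukopenia, fever and cough can each count both for and against the same child

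*Protocol*

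**What the plan says.** **Inclusion.** Protocol 5.1 requires at least three of four CABP criteria.

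- (i) "History of documented fever (rectal, ear, or oral temperature" at or above a stated limit, or hypothermia.
- (ii) "Acute onset or worsening within the previous 5 days of at least two of the following nine clinical signs and symptoms", of which cough is the first listed.
- (iii) "At least one of the five following laboratory findings". The list includes "leukopenia (4,500 WBC/mm³) and" then runs on to (iv).
- (iv) A new infiltrate on imaging, at the investigator's discretion. Protocol 8.2.4 adds: "The X ray is not mandatory and performed only for reference, as per investigators discretion".

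The severity score for acute bacterial rhinosinusitis (ABRS) in the same section gives 0 to 2 points to an item that combines bad mood and productive cough.

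**Exclusion.** Protocol 5.2 opens with "Participants will be excluded from the study if they meet any of the following exclusion criteria". No. 14 is "Evidence of leukopenia and/or thrombocytopenia". No. 21 is "Participants with symptoms suggestive of active COVID-19 infection (ie, fever, cough, etc" and the parenthesis closes there.

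**Surrounding rules.** Protocol 8 bars waivers, and Protocol 5.5 bars rescreening of screen failures. Protocol 9.2 sets a minimum of 68 CABP participants among 310. Protocol 9.4.2 and 9.4.3 report results overall and by indication.

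**The concern.** The amendment was written to bring CABP and ABRS into the study, yet two exclusions name findings that the CABP definition uses to establish eligibility. A site that follows both lists can reach opposite answers on the same child, and it has no waiver and no second screening with which to put the matter right.

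Two things are at stake. The first is whether the CABP group can be recruited as planned. The second is what it represents: if entry depends on how a site reads no. 21, the CABP rows of the safety and response tables describe a population that the protocol does not define.

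**Working it through.** The point is a comparison of texts; arithmetic enters only for context.

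**1. Planned CABP group.** Protocol 9.2 gives the ratio 18:9:14 (AOM, CABP, ABRS), total 41. 310 × 9/41 = 68.05, which reproduces the stated 68. Its share is 68/310 = 21.9%.

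**2. Leukopenia.** CABP (iii) counts leukopenia, printed with the figure 4,500 WBC/mm³, as a qualifying finding. No. 14 excludes leukopenia without giving a figure. One exclusion is enough, and no exception for CABP is stated. If both lines mean the same finding, a child who meets (iii) through leukopenia is excluded by no. 14.

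**3. Fever and cough.** Documented fever meets (i), and cough is one of the signs that count under (ii). No. 21 names both as symptoms that point to COVID-19. It asks for no test result and makes no exception for symptoms explained by the qualifying infection.

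**4. Search for a resolving rule.** None was found in Protocol 5.1, 5.2, 10.2 or 10.6, or in the SAP. Protocol 10.2 allows additional tests if the investigator thinks them necessary, but no SARS-CoV-2 test is mandated. Protocol 10.6.2 lists matters to weigh when enrolling during the pandemic. It does not say how to handle fever or cough in a child with a study infection.

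**5. What a literal no. 21 leaves open.** Meeting at least three of four criteria can happen in 4 + 1 = 5 ways: four sets of three, and all four together.

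- Criterion (i) is part of four of the five.
- The fifth, (ii)+(iii)+(iv), needs an infiltrate on an X-ray that is optional.
- Without (iv), the only route is (i)+(ii)+(iii).

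If current fever and cough both exclude, (i) must be met by an earlier documented fever or by hypothermia, or else the child must enter by (ii)+(iii)+(iv). In every case cough must be absent. Entry remains possible, but through less typical presentations.

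**6. ABRS.** A coughing child with ABRS also meets the words of no. 21. The ABRS threshold of 4 does not depend on cough, because the nasal discharge item alone can score 4.

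**7. Pooled primary endpoint.** Suppose TEAE incidence in the CABP children enrolled differs by d percentage points from that in the children intended. The pooled incidence then moves by (68/310) × d = 0.219d. The documents give no value for d, and this expression counts CABP only.

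**The case against.** **On no. 14**, a reader might infer that leukopenia excludes with certainty at every site, so that the leukopenia line in (iii) can never lead to enrolment. The documents do not prove this. No. 14 has no cut-off, the figure in (iii) carries no inequality sign in the text as read, and Protocol 8.2.3 has tests run at each site's local laboratory. If a local lower limit lies below 4,500, a child could satisfy (iii) without being called leukopenic under no. 14. The natural reading is still a conflict, because neither line refers to a second threshold.

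**On no. 21**, the wording leaves room for judgement about whether symptoms point to COVID-19. Protocol 10.6.2 asks sites to weigh individual benefit and risk when they decide on enrolment, which supports that reading. An amendment that adds CABP is unlikely to have meant to bar every coughing child. This objection stands in part: the literal reading is the less plausible one. But the same list marks judgement and exceptions where they are meant (no. 4 refers to clinical judgement, and no. 12 allows inhaled controller steroids), while no. 21 has no such clause. The judgement reading also leads directly to possible differences between sites.

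**On consequence**, there is no hypothesis test, the primary endpoint pools the indications, and the by-indication output is descriptive. That stands, and it limits the size of the point.

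Criterion (iii) announces five laboratory findings and three are legible. This may be an effect of text extraction, and nothing here rests on it.

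**Conclusion.** The conflict is in the text and should be fixed. On the natural reading, leukopenia both qualifies and excludes. Fever and cough both count for CABP entry and are named as grounds for exclusion, with no rule to separate the study infection from suspected COVID-19.

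Three stronger conclusions might be drawn, and the documents support none of them.

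- **CABP enrolment is impossible.** Other laboratory findings qualify, hypothermia or an earlier fever can meet (i), and cough is not required.
- **A number of children lost can be stated.** The documents give no frequency of these signs in CABP, so any such number would be invented.
- **The primary result is compromised.** It is one pooled incidence in which CABP carries 21.9% of the planned sample, and it is little affected.

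The practical cost falls on recruiting the 68 CABP children and on knowing which children the CABP summaries describe. The conclusion assumes that no. 14 and (iii) mean leukopenia in the same sense, and that the Study Reference Manual, which is not among the documents, does not settle either point.

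**What to change.** Reconcile exclusion 14 with CABP criterion (iii). Reconcile exclusion 21 with the CABP fever and cough criteria and with the ABRS productive-cough item, stating how signs attributable to the qualifying infection are treated. The aim is that one finding does not both qualify and exclude the same child. The clinical content is for the sponsor's clinical team.

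The cost is a short eligibility amendment. Under Protocol 10.1.1 it needs ethics committee approval before implementation. The analysis and the sample size do not change. The screen-failure information in Protocol 5.5 and the summary of reasons in SAP 9.1 are already planned and need no addition.
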